9. EVALUATIONS AND STATISTICAL METHODS

9.1. Evaluations

The following evaluations relating to tolerability, safety and clinical benefit will be made:

1. Adverse events (AEs) suspected to be related to injections of HGF plasmid
2. Discontinuations related to adverse effects from the injections of HGF plasmid
3. All AEs up to Month 3, Month 6, Month 12, and Month 18
4. Serious adverse events (SAEs) up to Month 3, Month 6, Month 12, and Month 18
5. Number of deaths and cause over the 18 month period up to Month 3, Month 6, Month 12, and Month 18
6. Number of subjects in whom the largest ulcer healed completely or gets smaller (photo confirmation) at 6, 12 and 18 months (cumulative)
7. Number of subjects in whom rest pain (based on the 100 mm VAS scale) reduces by 20 mm or more or was completely relieved at 6, 12 and 18 months (cumulative)
8. Change in VascuQol Questionnaire (QOL) score compared to the baseline at 6, 12 and 18 months
9. Number of subjects revascularized (bypass or endovascular intervention) up to Month 3, Month 6, Month 12, and Month 18
10. Number of subjects with minor and number of subjects with major amputations (at or above the ankle) up to Month 3, Month 6, Month 12, and Month 18

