This statistical analysis plan (SAP) provides a comprehensive and detailed description of strategy, rationale, and statistical methods to be used to assess clinical efficacy and safety. The purpose of the SAP is to ensure the credibility of the study findings in the pre-specified statistical approaches to the analysis of study data prior to the database lock. This SAP provides additional details concerning the statistical analysis outlined in the protocol.

2 Investigational Plan

A phase 3 study AG-CLI-0206 was planned as a registration study and received Special Protocol Assessment (SPA) approval by the U.S. Food and Drug Administration (FDA). Prior to undertaking the phase 3 study, a pilot study will confirm the feasibility of the study-related activities in study AG-CLI-0206 and the tolerability of the dosage regimen of AMG0001.

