2.4 Statistical and Analytical Procedures

2.4.1 General Statistical Considerations

This study is not powered for statistical inference, and any testing will be considered descriptive and exploratory. All data summarized in tabular form will have accompanying listings. Figures may also be provided.

Unless otherwise noted, the term “descriptive statistics” will refer to frequency and percent (%) for categorical data and number of observations (n), mean, standard deviation (SD), median, minimum, and maximum for continuous data.

Biodata (serum HGF protein) values reported as below the level of quantitation (10 copies/ uL) will be reported as BLQ and excluded in calculation of the mean and SD.

All analyses will be conducted using SAS 9.4 or later.

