2.4.3 Study Day, Analysis Visit Windows and Baseline

Subject visits will be analyzed by nominal visit and/or time point as recorded on the CRFs, given that the day on which the visit occurs falls into the appropriate window as described in the table below. If a visit date does not fall into the correct window, data from that visit will not be summarized in the tables, but it will be included in the listings.

Study Day will be calculated from the reference date, and will be used to show the start and stop day of assessments and events.

The reference date is defined as the day that the first injection is administered, that is, Day 0.

Study Day = (date of event – date of Day 0).

The analysis will utilize less stringent visit windows than defined in the protocol, as defined below. If a subject has more than one visit in a visit window, the visit closest to the scheduled day will be considered for the analyses. If the difference is a tie, the day before the scheduled day will be used in the statistical analyses.

Unless otherwise specified, baseline is defined as the last non-missing measurement taken prior to reference start date (excluding unscheduled assessments). In the case where the last non-missing measurement and the reference start date coincide, that measurement will be considered pre-baseline, but Adverse Events (AEs) and medications commencing on the reference start date will be considered post-baseline.

Unscheduled visit measurements will not be used to provide a measurement for either baseline values or post-treatment values. Unscheduled data will be included in the standard subject listings but not in the summary tables.

Table 2 Visit Window

Analysis Visit	Scheduled Day	Start of Window (Study day)	End of Window (Study day)
Screening	-30	-30	<0
Day 0	0	0	0
Month 3	90	80	100
Month 6	182	167	197
Month 9	273	258	288
Month 12	365	335	395
Month 15	455	420	490
Month 18	548	503	593
LTFU 1 (Month 24)	730	685	775
LTFU 2 (Month 30)	912	867	957
LTFU 3 (Month 36)	1095	1050	1140

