2.5.5 Efficacy Analysis

- Ulcer improvement**

A table showing the number of subjects completely healed in the target ulcer will be provided at up to 6 months, > 6 months to 12 months, from >12 months to 18 months. If available, the number of subjects with at least 20% reduction in bi-dimensional size (by measuring largest diameters) will be provided. The reduction in bi-dimensional size will be calculated by taking the product of the largest diameters for each baseline and postbaseline measurement, then subtracting the baseline result from the postbaseline result.

- Ischemic Rest pain (of the index leg) using a 10 cm VAS scale**

Rest pain severity will be assessed at the specified predetermined time points. Rest pain severity will also be assessed prior to surgical revascularization or major amputation (of the index leg). A table showing the number of subjects reduced by ≥ 20 mm from baseline in VAS score will be provided at up to 6 months, > 6 months to 12 months, from >12 months to 18 months. Summary statistics will be provided for baseline and change from baseline for each visit and LOCF. One sample t-test for change-from-baseline will be performed. If death occurs, the worst score prior to death instead of last observation will be carried forward.

- Hemodynamic Measurements**

Summary statistics will be provided for baseline and change from baseline for hemodynamic parameters (right/left brachial systolic pressure, ankle systolic pressure measured at dorsalis pedis and posterior tibial, toe systolic pressure, calculated ABI, and calculated TBI) by visit. At each visit, only subjects who have a non-missing value at both baseline and the specific visit will be summarized. Two-sided one-sample t-test will be performed for each visit and LOCF.

- Subjects with any worsening CLI event of index leg**

A summary table and listing of worsening CLI-related events of the index leg including any new or worsening events, worsening rest pain, new ulcer or worsening ulcer, new or worsening wound infection, peripheral vascular intervention, complication of a peripheral vascular intervention, cellulitis, and amputation due to worsening CLI will be provided.

- Subjects who either died, had MI, Stroke, revascularization (by surgical bypass, by endovascular intervention, by hybrid procedure), major amputation, or all-cause death**

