A summary table including counts and percentages and a listing will be provided for these parameters for the following time periods: up to Month 6, 0 to Month 12, and 0 to Month 18.

As a supplemental analysis, time to major amputation or death will be performed, and the Kaplan-Meier (KM) estimates with 2-sided 95% confidence interval using Greenwood's formula will be computed up to the end of the study and plotted. If a subject undergoes major amputation followed by death, it will be counted as an event. If a subject does not experience major amputation or death, the subject will be censored at the date of last contact as recorded on the CRFs.

- **Shift from baseline in Rutherford classification**

Shift from baseline in Rutherford classification will be summarized by study visit.

- **Quality of life (QoL)**

Quality of life (QoL) measurements will be assessed using the disease-specific vascular Quality-of-Life questionnaire (VascuQol). The VascuQol contains 5 domains (pain, symptom, activities, social, and emotional functioning), and responses are scored from 0 (lowest QOL imputed after death) to 7 (best QOL, maximum health). Responses are averaged for composite overall and domain-specific scores, giving equal weight to each question and domain. Subjects' data after revascularization or major amputation will be included in the analysis. However, after death, subjects will be scored as 0. For the effect of treatment on individual domains, pain, symptoms, and activity will be considered the most important of the 5 domains.

Summary statistics will be provided for baseline and change from baseline by visit for each score including total and domain scores. At each visit, only subjects who have a non-missing value at both baseline and the specific visit will be summarized, and two-sided one-sample t-tests for the change-from-baseline will be performed for each visit and LOCF.

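### SAP 2.5.5 counts pain and ulcer responders in separate intervals and under altered definitions, where Protocol 9.1 lists cumulative counts at 6, 12 and 18 months

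*SAP*

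**What the plan says.** Protocol 9.1 lists two responder counts.

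- Item 6 is the number of subjects whose "largest ulcer healed completely or gets smaller (photo confirmation) at 6, 12 and 18 months (cumulative").
- Item 7 is the number of subjects whose rest pain "reduces by 20 mm or more or was completely relieved at 6, 12 and 18 months (cumulative").

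SAP 2.5.5 handles both differently.

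- **Pain.** The table is specified as "reduced by ≥ 20 mm from baseline in VAS score will be provided at up to 6 months, > 6 months to 12 months", followed by a third interval from just after 12 months to 18 months. Complete relief does not appear.
- **Ulcer, healing.** Complete healing of the target ulcer (taken here to be the protocol's largest ulcer) is tabulated in the same three intervals.
- **Ulcer, shrinkage.** "If available, the number of subjects with at least 20% reduction in bi-dimensional size (by measuring largest diameters) will be provided". No time points are attached to this count. The size change is defined as the post-baseline product of diameters minus the baseline product.

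For death, MI, stroke, revascularization and major amputation, the same SAP section uses overlapping periods: "up to Month 6, 0 to Month 12, and 0 to Month 18". The opening section of the SAP describes its relation to the protocol this way: "This SAP provides additional details concerning the statistical analysis outlined in the protocol". Nothing in the SAP says that these two evaluations were meant to change.

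**The concern.** A cumulative count at Month 12 answers how many subjects have responded by then. An entry for the interval from 6 to 12 months answers either how many responded for the first time in that interval or how many were in response at some point during it. The SAP does not say which. Only the first-response meaning leads back to the protocol's figures.

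The definitions moved as well, so some subjects are responders under one document and not under the other. With about 8 to 10 subjects, one such subject visibly changes a reported percentage. If the SAP stays silent, someone must choose the counting rule after open-label data are in hand.

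**Working it through.** The plan states no figure to reproduce, so the check sets the two texts side by side and works through what each rule does to example subjects.

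**1. The two rules**

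| Element | Protocol 9.1 | SAP 2.5.5 |
|---|---|---|
| Pain rule | fall of at least 20 mm, or complete relief | fall of at least 20 mm only |
| Pain timing | cumulative at 6, 12, 18 months | up to 6, over 6 to 12, over 12 to 18 months |
| Complete healing | cumulative at 6, 12, 18 months | same three separate intervals |
| Ulcer smaller | any reduction, confirmed on photograph, cumulative | at least 20%, only if available, no time points |
| Subject counted once? | implied by cumulative | not stated |

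**2. Can the intervals be turned into cumulative counts?** Let the interval entries be a, b, c among N subjects.

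- First responses only: the cumulative counts are a, a+b, a+b+c.
- Response re-counted in each interval: Month 12 lies from max(a,b) to min(N, a+b), and Month 18 from max(a,b,c) to min(N, a+b+c).

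With N = 10 and assumed entries:

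| a, b, c | First-response reading (Months 6, 12, 18) | Re-counted: Month 12 | Re-counted: Month 18 |
|---|---|---|---|
| 3, 3, 3 | 3, 6, 9 | 3 to 6 | 3 to 9 |
| 4, 2, 1 | 4, 6, 7 | 4 to 6 | 4 to 7 |

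**3. Pain definition.** Take complete relief as VAS 0 with a baseline above 0. This is an assumption, since the protocol does not define it.

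- 15 mm to 0: fall of 15. Responder under the protocol, not under the SAP.
- 20 mm to 0: fall of 20. Responder under both.
- 60 mm to 40: fall of 20. Responder under both.
- 60 mm to 45: fall of 15. Responder under neither.

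The rules differ only for a subject with baseline above 0 and below 20 mm who becomes pain-free. Protocol 3.1 requires severe, opioid-treated rest pain for Rutherford 4 but admits Rutherford 5 subjects with or without rest pain. The realistic case is therefore a Rutherford 5 subject with mild pain.

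**4. Ulcer definition.** Example baseline 4 × 3 = 12 cm².

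- To 4 × 2.7 = 10.8 cm²: (12 − 10.8)/12 = 10%. Counts under the protocol; fails the 20% rule.
- To 3 × 3 = 9 cm²: (12 − 9)/12 = 25%. Counts under both.
- For the second case the SAP formula gives 9 − 12 = −3 cm². That is an absolute change and cannot be compared with 20% until it is divided by baseline.

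**5. Size of one reclassified subject, with all subjects as denominator.** 1/10 = 10 percentage points; 1/8 = 12.5 percentage points.

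**6. Which visits feed the tables?**

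- *Healing.* Protocol 5.18 has healing assessed at every study visit, and 5.17 makes the two-week confirmation an unscheduled visit. SAP 2.4.3 says: "Unscheduled data will be included in the standard subject listings but not in the summary tables". It also keeps visits outside their window out of the tables. Read literally, this would remove the confirmation visit.
- *Pain.* The visit lists in Protocol section 5 place VAS at Day 0 and Months 3, 6, 9, 12, 15 and 18. With 30-day months the post-baseline visits are days 90, 180, 270, 360, 450 and 540. All lie inside SAP Table 2 windows (80–100, 167–197, 258–288, 335–395, 420–490, 503–593). Protocol 4.11, however, asks for VAS at all visits, so the schedule itself is inconsistent.

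**The case against.** The strongest defence is that little depends on these tables. The primary objectives are feasibility, tolerability and safety, SAP 2.4.1 calls any testing descriptive and exploratory, and "All data summarized in tabular form will have accompanying listings", so the protocol's counts can be rebuilt. A first-response reading of the intervals is natural for healing, and on that reading the entries simply sum. Interval tabulation is also not peculiar to these endpoints: SAP 2.5.7 reports adverse events in successive periods where Protocol 9.1 item 3 says up to each month. All of this stands and keeps the point minor. It does not supply the missing counting rule or restore the dropped clauses.

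The 20% threshold can be defended as useful detail, because the protocol gives no rule for what counts as smaller. Tracings are scheduled only at Screening and Day 0, which may explain why the count is conditional on availability. That is a reason to keep the row, but it does not justify letting it silently replace the protocol's evaluation.

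Two stronger readings are tempting.

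- A reader might infer that half the visits are lost to these tables. By nominal day, 9 of the 18 scheduled visits after Day 0 (days 14, 28, 42, 104, 118, 132, 298, 312, 402) lie in no Table 2 window, and the closest-visit rule would drop days 284, 374 and 388 as well. The documents do not establish this. SAP 2.5.7 summarises physical examinations over ranges such as Day 0 to Day 42, so Table 2 is not applied everywhere. The response tables are by period, and the VAS visits in the section 5 lists all have windows.
- A reader might infer from the lack of a minimum entry VAS that the lost relief clause could affect every subject. The Rutherford 4 entry requirement makes that unrealistic.

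**Conclusion.** The point holds as a minor inconsistency in pre-specification. SAP 2.5.5 does not deliver the counts in Protocol 9.1 items 6 and 7. Its intervals yield the Month 12 and Month 18 figures only if they hold first responses, which it does not say. Two kinds of subject are responders under the protocol and not under the SAP:

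- a subject who becomes pain-free from a baseline VAS above 0 and below 20 mm;
- a subject whose ulcer shrinks by less than 20%.

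Each moves a percentage of all subjects by 10 to 12.5 points at N = 10 to 8. The documents do not show how many subjects are affected.

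This rests on reading complete relief as VAS 0 and on using all subjects as the denominator. The interval entries in the working are invented for illustration. No error rate, power figure or test depends on these counts.

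**What to change.** In SAP 2.5.5:

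1. Define pain response as a VAS reduction of at least 20 mm, or complete relief (VAS 0 with baseline above 0).
2. Tabulate subjects who have responded by Month 6, by Month 12 and by Month 18, each counted once. Use separate rows for pain response, complete healing of the largest ulcer, and largest ulcer healed or smaller than baseline on photograph.
3. Keep the reduction of at least 20% as an extra row where measurements exist, at the same time points, computed as (baseline product − post-baseline product) / baseline product.
4. State that healing may be counted from any study visit and from the unscheduled two-week confirmation visit, as an exception to SAP 2.4.3. Reconcile Protocol 4.11 with the visit lists on when VAS is taken.

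If the departure was intended, declare it in the SAP together with its counting rule.

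The cost is SAP wording, table shells and a small programming exception. No new visits are needed because ulcer photographs are already taken at each visit, but the row for smaller ulcers may require photographs to be re-read for size. Cumulative counts hide loss of response, and an apparent reduction can be photograph measurement noise, so by-visit status should stay in the listings.

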3.4. Administration of Study Product

Study product will be administered to subjects who were confirmed eligible by the Principal Investigator (eligibility will be confirmed by an entry committee) and whose CLI is stable (see Exclusion Criteria Section 3.3, item #1).

The study product will be administered by eight (8) intramuscular injections delivered to the index leg (see Section 3.2 Inclusion criteria for definition of index leg) at each dosing visit (see Table 1 Dosage Regimen above). For each of the 8 injections, 3 mL of AMG0001 will be injected in about 3 seconds. The precise anatomical location for study product injections will be based on vascular anatomy. The site will receive a detailed schema from the above entry committee indicating where the injection sites should occur. Duplex scanning must be used during the injection procedure to further clarify the injection sites.

Subjects will not be eligible to receive the subsequent doses of study product if a major amputation of the index leg has occurred. If the subject has been revascularized in the index leg, the Investigator should ensure that the subsequent doses of study product are not administered less than 1 month post-revascularization.

Analgesics may be administered prior to treatment injections. Local anesthetics applied to the skin are recommended. An anti-anxiety agent may be administered pre-dose to relieve any anxiety surrounding treatment procedures. Administration of analgesics is at the discretion of

the Investigator, but cannot be given to the subject prior to VAS pain scale measurement or Quality of Life (VascuQol Questionnaire) measurements. All analgesics given prior to injection should be accurately recorded on the appropriate Concomitant Medication CRF.

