8.1.2. SAEs Associated with Worsening CLI

Serious Adverse Events relating to the worsening of CLI that occur in the index limb such as gangrene, cellulitis or osteomyelitis, are related to the study disease and are symptoms/signs of progression of study disease will not be recorded as serious adverse events (unless the speed or extent of the symptoms/signs are unexpected based on the natural history or bear a strong temporal relationship to the study product as determined by the Investigator). Data on the subject's CLI status of the index limb will be recorded in detail on non-AE CRFs and is not required to be documented as an SAE. Frequently worsening of CLI may lead to hospitalization followed by local or systemic treatment or surgical intervention (minor amputation, surgical revascularization or major amputation). The entries for the above events will be made in the CLI section of the CRF. However, in the case of serious intercurrent illness or systemic complications like septicemia, multi-organ failure, or pneumonia, these events will be captured in the AE or SAE section of the CRF.

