9.2.2. Statistical Analysis for Efficacy and Safety

Categorical data will be summarized by the use of frequency tables showing the number and percentage of subjects falling within a particular category by visit, and detailed line listings of subjects will be provided.

Continuous data will be summarized by reporting number of observations, mean, standard deviation (SD), median, minimum and maximum by visit. Summary statistics will be provided for baseline and the change (with percent change) from baseline. A one-sample t-test will be performed on within group change-from-baseline for individual time point (Months 6, 9, 12, 15, and 18 with last observation data (assessed prior to intervention or worse score for deaths) carry-forward (LOCF)).

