2.4.2 Missing Data

For endpoints involving the VascuQoL assessment, non-missing data after revascularization or major amputation will be included in analysis, and missing values for subjects who are dead at the time point of interest will be scored as 0.

For the Visual Analogue Scale (VAS), each subject’s data after revascularization or major amputation will be imputed using the value of the last available assessment prior to intervention, and the worst score available will be imputed for assessments after death.

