2.5.7 Safety Analysis

- **Adverse Events**

Adverse event (AE) data will be collected using the standard AE CRF. All AEs will be coded using MedDRA dictionary version 16.1.

Treatment-emergent adverse events (TEAEs) will be evaluated, and a table showing the number and percentage of subjects with occurrences categorized by System Organ Class and Preferred Term will be provided by causality (relationship to study drug), whether the AE led to discontinuation, and whether the AE was deemed serious. For the causality, "Likely Related" and "Possibly Related" will be classified as "Related," and the most related AE will be summarized if multiple coded AEs occurred for the same subject. AEs that led to discontinuation and those that were deemed serious will be presented in separate columns. If a subject has more than one occurrence of the AE, the subject will be counted once. An additional table will be provided for the total number of AEs occurring during the study, presented by system organ class, causality, and severity, including all AEs, AEs from Day 0 up to Month 3, from Month 3 up to Month 6, from Month 6 up to Month 12, and Month 12 up to Month 18. To take the most conservative approach in categorizing severity during a period, the worst rating reported will be used in the

categorization. For example, if the severity is rated moderate one week and severe another week during the period, severe will be used as the severity rating category over the period.

Death or other serious AE (non-fatal MI or non-fatal stroke) are not in all cases recorded as an adverse event in the AE CRF, but could also be recorded in the outcome of adverse events. For those subjects who either died, had a serious AE, or discontinued participation in the study because of revascularization or other reason, a summary table and a subject line listing will be provided during the periods listed for the previous table along with the post-Month 18 LTFU period up to Month 24, Month 24-30 and Month 30-36.

- **Laboratory Data**

Listings of subjects with abnormalities will be provided with abnormal values flagged.

The following clinical laboratory tests will be listed:

- Hematology: including hemoglobin, hematocrit, RBC count, WBC count (total and differential) and platelet count.
- Urinalysis: including protein, glucose, blood, ketones, bilirubin, and microscopic examination.

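### The SAP neither applies nor withdraws the protocol's pre-intervention rule for index-leg pressures, ABI and TBI, so readings taken after revascularization can enter the by-visit t-tests

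*SAP*

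**What the plan says.** Protocol 9.2.2, under continuous data, sets one-sample t-tests of within-group change at Months 6, 9, 12, 15 and 18, based on "last observation data (assessed prior to intervention or worse score for deaths) carry-forward". The sentence names no endpoint.

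The SAP introduction describes its relation to the protocol: "This SAP provides additional details concerning the statistical analysis outlined in the protocol". SAP 2.4.2 then gives post-intervention rules for two endpoints only:

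- VAS: "data after revascularization or major amputation will be imputed using the value of the last available assessment prior to intervention", with the worst available score after death.
- VascuQoL: observed values after revascularization or major amputation are kept, and death is scored 0.

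The hemodynamics paragraph of SAP 2.5.5 covers ankle and toe pressures, ABI and TBI. Its only condition is that the subject has a value at baseline and at the visit. It then states: "Two-sided one-sample t-test will be performed for each visit and LOCF". Nothing says which value is carried forward.

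Protocol Table 3 (note 7) and section 5.15 require hemodynamic and VAS readings before a planned intervention. SAP 2.4.3 keeps unscheduled readings, and visits outside a Table 2 window, out of the summary tables.

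**The concern.** There is no control arm, so change from baseline is the only hemodynamic evidence the study will give. A successful revascularization raises pressure in the treated leg by itself. If such readings are averaged with the rest, the mean change mixes the effect of the procedure with any effect of AMG0001.

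The documents foresee these readings. Protocol 3.4 provides for continued dosing: "If the subject has been revascularized in the index leg, the Investigator should ensure that the subsequent doses of study product" must respect an interval after the procedure. Protocol 8.1.2 states: "Frequently worsening of CLI may lead to hospitalization followed by local or systemic treatment or surgical intervention", and its examples of surgical intervention include revascularization. Visits with hemodynamic measurements run to Month 18.

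**Working it through.** **Which rule applies to which measure**

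| Measure | Protocol 9.2.2 | SAP 2.4.2 | SAP 2.5.5 |
|---|---|---|---|
| VAS | pre-intervention value carried | same | repeats the death rule |
| VascuQoL | as above, by general wording | openly different: observed values kept | repeats the departure |
| Pressures, ABI, TBI | as above, by general wording | silent | all available baseline/visit pairs, plus undefined LOCF |

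The by-visit test therefore admits post-revascularization readings by a stated criterion. The LOCF test is ambiguous, because the term may or may not carry the protocol's meaning. Death and major amputation of the index leg leave no index-leg ankle or toe reading, so those subjects drop out of the by-visit test. Contamination comes from revascularization alone.

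**Shift in the mean ABI change**

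The documents give no revascularization rate and no expected gain. From the documents: n = 8 to 10; 0.06 as the index's measurement variability (Protocol Appendix B); 0.1 as a marked change (Protocol 5.2).

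Without assuming a rate or a gain, the mean moves by 0.06 once the revascularized subjects' gains add up to 0.06 × 8 = 0.48 or 0.06 × 10 = 0.60. It moves by 0.1 once they add up to 0.8 or 1.0.

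For a range, assume r = 1 or 2 subjects revascularized, a gain g of 0.2, 0.3 or 0.5, and no drug effect. The shift is r × g / n:

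| | g = 0.2 | g = 0.3 | g = 0.5 |
|---|---|---|---|
| n = 8, r = 1 | 0.025 | 0.0375 | 0.0625 |
| n = 8, r = 2 | 0.05 | 0.075 | 0.125 |
| n = 10, r = 1 | 0.02 | 0.03 | 0.05 |
| n = 10, r = 2 | 0.04 | 0.06 | 0.10 |

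The shift is below 0.06 in 7 of 12 combinations, 0.06 or more in 5, and 0.1 or more in 2. Carrying the pre-intervention value forward gives an expected shift of 0 in all 12.

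**Effect on the t-test**

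The 12 combinations were simulated with two assumed SDs of change, 0.06 and 0.085 (0.06 × √2), giving 24 settings with 200,000 trials each and a two-sided test at an assumed 5% level. Rejection ranged from about 0.05% to 8.6%. It exceeded 5% in 6 settings, all with two revascularized subjects: gain 0.2 (four settings), and gain 0.3 with SD 0.085 (two settings). It never exceeded 5% with one.

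The reason is that an outlying value raises the SD as well as the mean. With no other variation, one subject with gain g gives mean g/n and standard error g/n, so t = 1 whatever the gain. Two such subjects give t = √(2(n − 1)/(n − 2)), which is 1.53 for n = 8 and 1.50 for n = 10. The two-sided 5% critical values are 2.36 and 2.26.

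**Whether the pre-intervention reading is usable**

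SAP Table 2 windows cover 21 + 31 + 31 + 61 + 71 + 46 = 261 of study days 1 to 548. The other 287 (52%) fall in no window. Counted to the end of the Month 18 window (day 593), it is 287/593 = 48%. These are calendar days, not intervention dates, but they show that a pre-intervention reading can easily fall outside a window.

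**The case against.** The best defence is that the plan as a whole does have a rule. Protocol 9.2.2 covers continuous data, and the SAP says it adds detail to the protocol. A reader might infer that no rule exists at all; that would be wrong. What stands is that the SAP restates the rule for VAS only, and its by-visit criterion for hemodynamics conflicts with it.

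One can also doubt that the protocol rule was meant for pressures. Hemodynamics are not among the ten items introduced by "The following evaluations relating to tolerability, safety and clinical benefit will be made" in Protocol 9.1, and a worse score for deaths fits a scale better than a pressure. The doubt about deaths is fair, and it is a reason not to impute a pressure after death. It does not settle which value to use after a revascularization.

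Analysing observed values is a recognisable descriptive choice, and the SAP makes it for VascuQoL. But there it says so.

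The doubt about the pre-intervention reading is narrow. Protocol 5.17 describes unscheduled visits in other terms, and 5.15 makes these readings a required set. For VAS, SAP 2.4.2 refers to the last available assessment, and 2.5.5 mentions a rest-pain assessment before surgery. The documents do not support saying that the reading is excluded as unscheduled. Only the out-of-window question remains.

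Finally, with 8 to 10 subjects, the listings and the revascularization table let a reader find those affected. They do not correct the mean.

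**Conclusion.** The point holds as an inconsistency between protocol and SAP that can bias a descriptive mean upward. The size is 0.02 to 0.125 in mean ABI change under the assumed 1 to 2 revascularizations and gains of 0.2 to 0.5. More than half of those combinations stay below the protocol's own 0.06 variability figure.

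Two stronger readings are tempting and not supported. One is that the gap creates a general false-positive risk: two-sided rejection exceeds 5% in only 6 of 24 assumed settings. The other is that deaths and amputations also contaminate the by-visit tests: they leave no reading to enter.

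The impact is modest. SAP 2.4.1 calls all testing exploratory, and hemodynamics are outside the primary objectives. There is no bias if no index leg is revascularized, or if such subjects leave follow-up. SAP 2.5.7 foresees the latter for some, who "discontinued participation in the study because of revascularization or other reason". Entry as no-option or poor-option subjects also limits how often revascularization happens. The change is still worth making, because it is cheap and settles before database lock a choice otherwise left to the analysis.

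**What to change.** - In SAP 2.4.2 and 2.5.5, state that the Months 6 to 18 t-tests and LOCF for index-leg ankle pressure, toe pressure, ABI and TBI use the last value before index-leg revascularization or major amputation, as Protocol 9.2.2 provides.
- Keep the observed by-visit summary as a supplementary table, with post-intervention values flagged and the affected subjects counted.
- In SAP 2.4.3, state that the pre-intervention reading required by Protocol Table 3 note 7 and section 5.15 may serve as that last value for hemodynamics and VAS, even outside a Table 2 window.
- Do not impute a pressure after death. State that the protocol's worse-score wording is applied to VAS only, and report the number of deaths beside the hemodynamic results.

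The cost is one SAP paragraph, one sentence in 2.4.3 and one extra table; data collection does not change. The mean change may look less favourable. Carry-forward also hides real change after an intervention, which is why the observed table stays.
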